3.6 Treatment assignment and treatment groups

At Baseline, eligible subjects will be assigned as described in [Section 2.3.2](#). Summaries using the FAS will be based on treatments according to the assignment and not actual treatment received.

It is expected that subjects will receive treatment as assigned. Hence, safety analyses should be based on assigned treatment for the SS. However, if it is determined after unblinding that subjects assigned to placebo received bimekizumab at any time, then these subjects will be reallocated to the appropriate bimekizumab group and will be summarized accordingly from the time point at which the misallocation occurred. If a subject receives different doses of bimekizumab at different time points, then the subject will be allocated to the highest dose received. If the highest dose was received earlier than the other(s), then all safety data will be summarized under that dose. If the highest dose was received later than the other(s), then safety data will be summarized under that dose starting from the time point at which it was first received. Since the period of exposure at risk includes an additional 140 days following the last dose of study medication, no consideration is given to the time at which exposure to misallocated doses can be considered complete.

Subjects assigned to a bimekizumab group will only be reallocated to the placebo treatment group if they never received bimekizumab.

Because subjects entering PS0011 may or may not be continuing on the same dose as that received in PS0010, there are various combinations of treatment that could be received when considering both PS0010 and PS0011 together. For describing the summaries to be produced, treatment groups will be categorized as either the PS0011 treatment groups or PS0010/PS0011 treatment groups. The categorizations are outlined below.

PS0011 treatment groups

This refers to the study treatment assigned to the subject at the beginning of PS0011 and does not account for the treatment received in PS0010. The PS0011 treatment groups are as follows:

- Placebo
- Bimekizumab 64mg Q4W
- Bimekizumab 160mg Q4W
- Bimekizumab 320mg Q4W
- All Bimekizumab (optional – to be used only if specified)

PS0010/PS0011 treatment groups

This refers to the combination of the randomized treatment in PS0010 and the treatment assigned at the beginning of PS0011. Some groups have been combined where it is considered appropriate to do so. The PS0010/PS0011 treatment groups are as follows:

- Placebo to Placebo
- Placebo to Bimekizumab 160mg Q4W
- Bimekizumab 64mg Q4W to Bimekizumab 64mg Q4W
- Bimekizumab 64mg Q4W to Bimekizumab 160mg Q4W
- Bimekizumab 160mg Q4W to Bimekizumab 160mg Q4W – note that the PS0010 160mg Q4W groups with and without the loading dose are both included here
- Bimekizumab 160mg Q4W to Bimekizumab 320mg Q4W – note that the PS0010 160mg Q4W groups with and without the loading dose are both included here
- Bimekizumab 320mg Q4W to Bimekizumab 320mg Q4W
- Bimekizumab 480mg Q4W to Bimekizumab 320mg Q4W

The treatment groups to be used in the presentations of safety and efficacy will depend on the objective of the summaries and will be specified accordingly.

3.7 Center pooling strategy

Centers will be pooled into regions for analysis purposes. Centers will be grouped in the following regions: North America, Europe and Asia. These regions include the following countries:

- North America: Canada, USA
- Europe and Asia: Czech Republic, Hungary, Poland, Japan

3.8 Coding dictionaries

All prior and concomitant medications other than study drug will be classified by World Health Organization (WHO) Anatomical Therapeutic Chemical (ATC) Classification, presenting Anatomical Main Group (ATC Level 1), Pharmacological Subgroup (ATC Level 3), and preferred term, using version SEP/2015 of the WHO Drug Dictionary, according to UCB standard operating procedures (SOPs).

All adverse events (AEs) will be classified by primary system organ class (SOC), high level term (HLT) and preferred term (PT) using version 19.0 of the Medical Dictionary for Regulatory Activities (MedDRA®) according to UCB SOPs. Previous and ongoing medical history will be classified by MedDRA® SOC and PT.

3.9 Analysis time points

3.9.1 Double-blind treatment period

The double-blind treatment period begins at the Baseline visit (Week 0) at the time of first study medication administration (inclusive) and ends at the Week 48/withdrawal visit.

Subjects will be classified as completing the study if they complete the Week 48 visit without withdrawal from the study. This is regardless of whether they attend the SFU visit.

3.9.2 Follow-up period

The SFU visit will take place 20 weeks after the last dose of study medication.

3.10 Relative day

The relative day will be included in different listings and will be calculated as follows:

- If the start (stop) date occurred on or after the first dose, but prior to the double-blind drug stop date, relative day is calculated as start (stop) date minus first dose + 1
- If the start (stop) date occurred after the last dose of double-blind drug, the relative day to the most recent dose is calculated as start (stop) date minus most recent dose date. The relative day in this situation should be preceded by a '+'
- If the start (stop) occurred before the first dose, the relative day is calculated as start (stop) date minus first dose date. The relative day in this situation should be preceded by a '-'.

3.11 Changes to protocol-defined analyses

There have been no changes to the protocol-defined analyses.

4 STATISTICAL/ANALYTICAL ISSUES

4.1 Adjustments for covariates

Not applicable.

4.2 Handling of dropouts or missing data

4.2.1 Handling missing data for the safety analyses

For analyses of AEs and concomitant medication usage, a complete date must be established in order to correctly identify the AE or medication as occurring during treatment or not. For purposes of imputing missing components of partially-reported start and stop dates for AEs and for medication use, the algorithms listed below will be followed. Start and stop dates of AEs or concomitant medication will be displayed as reported in the subject data listings (ie, no imputed values will be displayed in data listings).

Partial AE and concomitant medication start dates will be imputed as follows:

Imputation of Partial Start Dates

- If only the month and year are specified and the month and year of first dose is not the same as the month and year of start date, then use the 1st of the month
- If only the month and year are specified and the month and year of first dose is the same as the month and year of the start, then use the date of first dose
- If only the year is specified, and the year of first dose is not the same as the year of the start date, then use the 1st of January of the year of the start date
- If only the year is specified, and the year of first dose is the same as the year of the start date, then use the date of first dose
- If the start date is completely unknown and the stop date is unknown or not prior to the date of first dose, then use the date of first dose.

Imputation of Partial Stop Dates

- If only the month and year are specified, then use the last day of the month

- If only the year is specified, then use December 31st of that year
- If the stop date is completely unknown, do not impute the stop date.

In the event of ambiguity or incomplete data which makes it impossible to determine whether a medication was concomitant or an adverse event was treatment emergent, the medication will be considered as concomitant or the adverse event will be considered treatment emergent.

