8.1 Statistical analysis of the primary safety variable

8.1.1 Derivation of TEAEs

An AE is any untoward medical occurrence in a subject or clinical investigation subject administered with a pharmaceutical product that does not necessarily have a causal relationship with this treatment. An AE can therefore be any unfavorable and unintended sign (including an abnormal laboratory finding), symptom, or disease temporally associated with the use of a medicinal (investigational) product, whether or not related to the medicinal (investigational) product.

TEAEs are defined as those AEs that have a start date on or following the first administration of study treatment in PS0011 through the final administration of study treatment + 140 days (covering the 20-week SFU period). If it is not possible (due to partial dates) to determine whether or not an AE is treatment-emergent then it will be assumed to be a TEAE. TEAEs will be categorized to the treatment group based on the dose being received at the time of onset of the event.

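### SAP 4.2.1 moves partially dated AE starts to the first-dose date without checking the stop date, so a few AEs that ended before the first PS0011 dose would count as treatment-emergent

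*SAP*

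**What the plan says.** SAP 4.2.1 lists five rules for partial start dates of AEs and medications and makes them binding: "the algorithms listed below will be followed". Three of them can return the date of first dose:

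- Month and year known, same month as first dose: if "the month and year of first dose is the same as the month and year of the start, then use the date of first dose".
- Year only, same year as first dose: "If only the year is specified, and the year of first dose is the same as the year of the start date", the first-dose date is used.
- Nothing known: "If the start date is completely unknown and the stop date is unknown or not prior to the date of first dose", the first-dose date is used.

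Only the last of these looks at the stop date.

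SAP 8.1.1 defines TEAEs by start date alone, as AEs that "have a start date on or following the first administration of study treatment in PS0011", up to 140 days after the last dose. Two fallback sentences lean towards inclusion. The one in 4.2.1 begins "In the event of ambiguity or incomplete data which makes it impossible to determine whether a medication was concomitant" and also covers AEs. The one in 8.1.1 begins "If it is not possible (due to partial dates) to determine whether or not an AE is treatment-emergent". Both apply only where the status cannot be determined.

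SAP 8.1.4 counts subjects with the AE and stops their time at risk at its first occurrence. SAP 8.1.5 counts all events over total time at risk. Together these give the primary safety summary in SAP 8.1.6.

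**The concern.** The stop-date check is present where least is known about the start and absent where more is known. An AE with no start date and a stop before first dose is not moved. The same AE with its month recorded can be moved to the first-dose date, after its own end. The stop date has already settled that it was not treatment-emergent, so there is no ambiguity for a conservative rule to resolve.

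Such AEs can be in the PS0011 data. Protocol 9.1.1 records AEs from consent, and Protocol Table 5–1 (footnote c) places PS0011 consent at PS0010 Week 8 or Week 12, before the first PS0011 dose.

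A false TEAE adds to the event count, may add a subject to the incidence numerator, and cuts that subject's time at risk for the AE. An imputed start on the dosing day also meets the timing condition for hypersensitivity and anaphylactic reactions in SAP 8.2.1, although the preferred-term conditions must still be met. SAP 4.2.1 keeps imputed dates out of the listings, so a start after a stop would not be seen there.

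**Working it through.** The plan states no figure to reproduce. The check applies the rules as written.

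**One case (illustrative dates).** First dose 20 March 2017, start recorded as March 2017, stop 10 March 2017.
- As written: the start becomes 20 March, so the AE is a TEAE with duration 10 − 20 + 1 = −9 days.
- With a stop-date condition and the 1st of the month as substitute: the start becomes 1 March, so it is not a TEAE and its duration is 10 days.
- Start wholly unknown, same stop: not moved to first dose, so not a TEAE.

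**Share misclassified, given a partial start date.** Take every pair start ≤ stop < first dose within W days before first dose, weighted equally, for each first-dose date in a 365-day year. The AE escapes the rule only if its start lies in an earlier period than the first dose. With k period boundaries a year (1 for year-only, 12 for month and year), a start a days before first dose escapes for k × a of the 365 dates, and there are a such pairs. For W up to 28 this gives

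share classed as TEAE = 1 − k(2W + 1)/(3 × 365).

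| W (days) | Year only | Month and year |
|---|---|---|
| 7 | 1 − 15/1095 = 98.6% | 1 − 180/1095 = 83.6% |
| 14 | 1 − 29/1095 = 97.4% | 1 − 348/1095 = 68.2% |
| 28 | 1 − 57/1095 = 94.8% | 1 − 684/1095 = 37.5% |

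For a full start date, or a wholly unknown start with a known stop, the share is 0%. With the stop-date condition added, it is 0% throughout. These shares are conditional on a partial start date and a stop before first dose. They do not estimate how often that occurs.

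**Effect of one false event on the incidence rate.** SAP 7 expects 24 injections, two per visit, so 12 dosing visits from Week 0 to Week 44, with the last on day 308. By SAP 8.1.3, exposure at risk is 308 + 140 = 448 days = 64 weeks, which matches the stated maximum study duration. In years, T = 448/365.25 = 1.2266. The false event falls on day 1, so the denominator loses 447/365.25 = 1.22 years.

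The documents give no group sizes, so N and the true event counts are assumptions. Every subject has full exposure, and true events occur at mid-exposure (T/2).

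- N = 5, 0 to 1 subject: 0 becomes 100/(4T + 0.003) = 20.4.
- N = 15, 1 to 2: 100/(14.5T) = 5.6 becomes 200/(13.5T + 0.003) = 12.1.
- N = 40, 1 to 2: 100/(39.5T) = 2.1 becomes 200/(38.5T + 0.003) = 4.2.
- N = 120, 3 to 4: 300/(118.5T) = 2.1 (95% CI 0.4 to 6.0) becomes 400/(117.5T + 0.003) = 2.8 (0.8 to 7.1).

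Rates are per 100 subject-years; the intervals use SAP formulas 11 and 12.

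**Medications.** Under SAP 6.4, Prior means started before study medication, and Concomitant means at least one day shared with the dosing period. A drug stopped before the first PS0011 dose, with its start imputed to that dose, meets neither definition relative to PS0011.

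**The case against.** The strongest reply is that a sensible programmer would not apply the rule this way. The aim of SAP 4.2.1 is correct classification, and SAP 8.1.1 assumes treatment emergence only when the status cannot be determined; a known earlier stop date determines it. That supports a reasonable reading, but it is not a rule. The algorithm is binding, the TEAE definition looks only at the start date, and both fallbacks can only add TEAEs.

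Other replies limit the point, and they stand:

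- SAP 4.2.1 does not say which study's first dose is meant. SAP 6.4 uses both. PS0011 is the natural reading for PS0011 TEAEs. If PS0010 were meant, these AEs would be dated before PS0011, but a true PS0011 TEAE known only to the month of the first PS0011 dose would go to the 1st of that month, possibly before the dose. Either reading needs an edit.
- The incidence numerator counts subjects. A subject who has the same AE again on treatment adds nothing to it; only the time to first event is shortened.
- In the combined PS0010/PS0011 tables (SAP 8.2.1), AEs on the PS0011 Baseline date go mostly to the PS0010 treatment. The charge against the new dose concerns the PS0011-only tables.
- The study is descriptive, and the error over-counts TEAEs.

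A reader might infer from the year-only rule that AEs from up to 12 months before first dose are at risk. The documents do not support this. PS0011 AE recording starts at consent, about 4 weeks before first dose at most, and even merged PS0010 records would bring in a 12-week treatment period. A reader might also infer that medications become falsely concomitant. They do not, because a drug stopped before first dose shares no day with dosing.

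**Conclusion.** The rule is wrong as written, and the point is minor. Two of the five start-date rules can give an AE a start after its known end and make it a TEAE in the PS0011 EAIR and EAER, with time at risk for that AE of about 1 day in the incidence rate. For medications, the consequence is possible loss of Prior status relative to PS0011.

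The size cannot be estimated, because the documents do not say how often partial dates occur. The error needs a partial start date in the same month or year as first dose and a stop before it, within about 0 to 4 weeks unless PS0010 AE records are merged. One false event matters visibly only in a small group or for a rare term. The conclusion assumes that first dose means the first PS0011 dose.

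**What to change.** In SAP 4.2.1:

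1. Add to the month-and-year and year-only same-period rules the condition already used for wholly unknown starts: the first-dose date applies only if the stop date is unknown or falls on or after first dose.
2. State that otherwise the 1st of the month, or 1 January, is used. This must be written out, because the wholly-unknown rule supplies no substitute date when the stop is earlier.
3. Name PS0011 as the study whose first dose applies for PS0011 TEAEs.

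The cost is a clause in each of two rules, one clarifying sentence and a small programming change. A count of records whose imputed start falls after the recorded stop would show whether any result is affected. The inclusive treatment of truly ambiguous dates stays as it is.

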4.2.2 Handling missing data for the efficacy analyses

For the planned efficacy analysis, missing responder data will be imputed using non-responder imputation (NRI). That is, subjects that discontinue study medication early or who have missing data at a given time point will be counted as non-responders. Summaries based on observed case data will also be prepared.

Continuous efficacy variables will be imputed using multiple imputation (MI) via the Markov-Chain Monte Carlo (MCMC) method. Summaries based on observed case data will also be prepared.

The MI procedure for continuous efficacy variables (based on MCMC) will be applied as follows:

1. Create a dataset, one for each treatment group, of subjects with observed values and those needing estimation by multiple imputation. The missing values in each dataset will be filled in using the MCMC method with a total of 100 sets of imputations being performed. Values at Baseline and at each post-Baseline visit will be included in the imputation model in chronological order with prior biologic exposure and region as factors. The resulting datasets for each treatment arm will be combined into one complete dataset based on each of the 100 imputations.

Note: The imputation model based on the MCMC method will only allow continuous variables in the imputation model. Therefore, prior biologic exposure and region will be re-coded as indicator variables (with values of 0 or 1 for each level of the variable). In order to achieve model convergence, prior biological exposure may be dropped from the model, if convergence is still not obtained then region may also be dropped from the model.

2. The relevant change from Baseline (or percent change from Baseline) values will then be derived based on the imputed datasets and will be summarized by imputation.
3. The summary statistics from each of the 100 imputed datasets will be combined for the calculation of means and standard deviations using Rubin's rules, which account for the uncertainty associated with the imputed values (Rubin, 1987). This will be done using SAS PROC MIANALYZE. For calculation of other descriptive statistics such as the median, min and max, Rubin's rules do not apply. Multiple imputation estimates will be computed by simply averaging the estimates from the $m = 1, \dots, M$ independent repetitions of the imputation algorithm:

$$\bar{\theta} = \frac{1}{M} \sum_{m=1}^M \hat{\theta}_m$$

where $\hat{\theta}_m$ = estimate of θ from the completed dataset $m = 1, \dots, M$.

There may be cases where the multiple imputation model fails to converge (eg, sparse subgroups). In such situation, the LOCF approach will instead be used to impute missing data. If LOCF is used instead of multiple imputation for this reason, this will be clearly specified in the corresponding table summary. Should there be no missing data for a study variable then only observed case data will be produced.

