6.3 Withdrawal criteria

Subjects are free to withdraw from the study at any time, without prejudice to their continued care.

Subjects should be withdrawn from the study and will be asked to complete the Early Withdrawal Visit and SFU Visit (20 weeks after the last received dose) if any of the following events occur:

1. Subject withdraws his/her consent.
2. There is confirmation of a pregnancy in a female subject during the study, as evidenced by a positive pregnancy test.
3. The Sponsor or a regulatory agency requests withdrawal of the subject.
4. Subject develops an illness that in the opinion of the Investigator would interfere with his/her continued participation if the risk of continuing participation outweighs the potential benefit.
5. Subject develops erythrodermic, guttate, or pustular form of psoriasis.
6. Subjects considered to have either a suspected new latent tuberculosis (LTB) infection or who develop an active TB or NTMB infection during the study (including but not limited to, conversion demonstrated by IGRA or other diagnostic means) must be immediately discontinued from study medication; an Early Withdrawal Visit must be scheduled as soon as possible, but not later than the next regular visit.

Confirmed active TB is an SAE and must be captured on an SAE Report Form and provided to the Sponsor in accordance with SAE reporting requirements. As with all SAEs, periodic

follow-up reports should be completed as per protocol requirements until such time as the TB infection resolves.

Additional information on TB policies are provided in [Section 9.8.1](#).

7. Subject is noncompliant with the study procedures or medications in the opinion of the Investigator.
8. Subject uses prohibited concomitant medications, with the exception of topicals, as defined in this protocol ([Section 7.8.2](#)), that may present a risk to the safety of the subject in the opinion of the Investigator and/or the Medical Monitor.
9. Subject has a clinical laboratory value meeting the following criteria:
 - Common Terminology Criteria for Adverse Events (CTCAE) Grade 3 and above: subjects must be withdrawn regardless of relationship to study drug or duration of event.
 - CTCAE Grade 2

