 - Subjects may remain in the study if the event is transient. If a subject has a Grade 2 laboratory abnormality, a retest is required within 1 to 2 weeks at a scheduled or unscheduled visit. If the repeat value is below Grade 2, the subject may receive the next scheduled study treatment. If the value on the repeat is still Grade 2 or above, a second repeat test must be performed and results made available prior to the next scheduled study treatment. If this second repeat value is still Grade 2 or above, the subject must be withdrawn.
10. Subject has active suicidal ideation as indicated by a positive response (“Yes”) to questions 4 or 5 or to the suicidal behavior questions of the “Since Last Visit” version of the self-rated electronic Columbia-Suicide Severity Rating Scale (eC-SSRS). The subject should be referred immediately to a Mental Healthcare Professional and must be withdrawn from the study.
11. Subjects with a HADS-D score ≥ 15 must be withdrawn. Any subject who develops a HADS-D score of >10 during the study should be referred immediately to a Mental Healthcare Professional for further evaluation and potential withdrawal by the Investigator.
12. Subject does not achieve PASI75 at Week 12 or later following study treatment in PS0011.
13. Subject experiences an AE as described below:
 - Any CTCAE Grade 3 and above adverse event (AE) that is assessed as related to study drug in the opinion of the Investigator
 - If the event is deemed to be not related to study drug by the Investigator, the subject may remain in the study after approval by the Medical Monitor.
 - Any CTCAE Grade 2 event that is evaluated as related to study drug in the opinion of the Investigator, is persistent, and falls into any of the following System Organ Classes (SOCs): “Blood and lymphatic disorders,” “Cardiac disorders,” or “Vascular disorders.”
 - Persistent is defined as lasting 28 days or more, which spans at least 2 scheduled injections.

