7.8.2 Prohibited concomitant treatments (medications and therapies)

The list of prohibited concomitant medications is provided [Table 7-1](#).

Table 7-1: Prohibited psoriasis medications during PS0011

Drug
Systemic retinoids
Systemic treatment (non-biological): systemic immunosuppressant agents (eg, methotrexate, cyclosporine, azathioprine, thioguanine) systemic fumarate systemic corticosteroids phototherapy or chemophototherapy
Anti-TNFs: infliximab (including biosimilar), golimumab etanercept (including biosimilar) certolizumab pegol adalimumab (including biosimilar)
Other biologics and other systemic therapies: apremilast ustekinumab
Anti-IL-17 therapy
Any other antipsoriatic agent (systemic)
Any other antipsoriatic agent (topical) under investigation

IL=interleukin; TNF=tumor necrosis factor

Subjects who take prohibited medications may be withdrawn from study treatment but followed until the SFU Visit. The decision to withdraw a subject for taking prohibited medications should be made in consultation with the Medical Monitor.

Vaccines

Administration of live (including attenuated) vaccines is not allowed during the conduct of the study or for 20 weeks after the last dose of study drug. Administration of inactivated vaccines is allowed during the study at the discretion of the Investigator.

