14.6 Planned efficacy analyses

Efficacy variables will be summarized based on the FAS. The summaries described in this section will provide data on maintenance of effect of study treatment over 48 weeks.

Responder efficacy variables (PASI75, PASI90, PASI100, IGA, and DLQI score of 0 or 1) will be summarized descriptively using counts and percentages by scheduled visit and PS0010/PS0011 treatment group. The PASI responder variables will be derived relative to both the PS0010 Baseline and the PS0011 Baseline with responder rates being presented side-by-side in applicable summary tables. Missing data will be handled by using nonresponder imputation (NRI), meaning that subjects that discontinue early or who have missing data at a given time point are imputed as though they did not achieve the given response. Supportive summaries will be based on observed case data.

Continuous efficacy variables based on the change from Baseline (PASI, DLQI, BSA, mNAPSI, PSSI, PGADA, SF-36, and HADS) will be summarized using descriptive statistics by scheduled visit and PS0010/PS0011 treatment group. The table presentations will display descriptive statistics for the PS0010 Baseline, followed by descriptive statistics for the observed, change from PS0010 Baseline, and change from PS0011 Baseline results by scheduled visit for PS0011. Figures for selected variables will also be generated in order to demonstrate the kinetics of response over time. Missing data will be handled by using multiple imputation (MI) via the Markov-Chain Monte Carlo (MCMC) method. Supportive summaries will be based on observed case data.

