If a subject has experienced an improvement, this measure will be positive. If a subject has experienced a worsening in their condition, this measure will be negative.

If a subject is missing one or two severity measurements for a certain region, the average of the remaining severity measurement(s) within that region will be utilized to substitute for the missing severity measurement(s) in that region. If the area of affected skin and/or all severity measurements for up to two regions are missing, then the missing $(R + T + S) \times A$ for a region will be substituted by the average of the available $(R + T + S) \times A$. Otherwise, the PASI will be set to missing.

A categorical variable, PASI90 response, is defined to be equal to 1 if the percentage improvement from Baseline in the PASI scores is 90% or greater and 0 if the percentage improvement from Baseline is less than 90%. This definition is introduced for the purpose of identifying subjects who respond to the treatment (1 = responder, 0 = non-responder). Similarly, the categorical efficacy variables PASI75 and PASI100 response are equal to 1 for subjects with improvements of 75% or greater and 100% from Baseline in PASI score respectively, and equal to 0 otherwise.

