10.1.2 IGA response

10.1.2.1 Derivation of IGA response

A static IGA for psoriasis will be used to assess disease severity in all subjects during the study.

The Investigator will assess the overall severity of psoriasis using the following five-point scale (see [Table 10-1](#)):

Table 10–1: Five-point Investigator's Global Assessment

Score	Short Descriptor	Detailed Descriptor
0	Clear	No signs of psoriasis; post-inflammatory hyperpigmentation may be present
1	Almost clear	No thickening; normal to pink coloration; no to minimal focal scaling
2	Mild	Just detectable to mild thickening; pink to light red coloration; predominately fine scaling
3	Moderate	Clearly distinguishable to moderate thickening; dull to bright red, clearly distinguishable to moderate thickening; moderate scaling
4	Severe	Severe thickening with hard edges; bright to deep dark red coloration; severe/coarse scaling covering almost all or all lesions

IGA response is defined as clear (0) or almost clear (1) with at least a two category improvement from Baseline.

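### Taking a prohibited systemic therapy, biologic or phototherapy does not make a subject a non-responder, so a subject kept on study drug while using one can count as a PASI90 or IGA responder (minor)

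*SAP*

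**What the plan says.** **Non-response.** In SAP 4.2.2, "subjects that discontinue study medication early or who have missing data at a given time point will be counted as non-responders". Protocol 14.6 agrees: "subjects that discontinue early or who have missing data at a given time point are imputed as though they did not achieve the given response". Neither section names a third trigger.

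**Responder definitions.** PASI90 response "is defined to be equal to 1 if the percentage improvement from Baseline in the PASI scores is 90% or greater" (SAP 10.1.1.1). For the other secondary variable, "IGA response is defined as clear (0) or almost clear (1) with at least a two category improvement from Baseline" (SAP 10.1.2.1). Both depend on scores alone.

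**What follows from taking a Table 7-1 therapy.**
- Protocol 7.8.2: "Subjects who take prohibited medications may be withdrawn from study treatment but followed until the SFU Visit". The decision is to be made in consultation with the Medical Monitor.
- Protocol 6.3, criterion 8, covers prohibited use "that may present a risk to the safety of the subject in the opinion of the Investigator and/or the Medical Monitor".
- Protocol 6.3, criterion 7: "Subject is noncompliant with the study procedures or medications in the opinion of the Investigator".
- Protocol 6.3, criterion 12, applies whatever the medication: "Subject does not achieve PASI75 at Week 12 or later following study treatment in PS0011".

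**Other uses of the information.** The only analysis consequence that SAP 3.4 attaches to the deviation review is exclusion from the PK-PPS. SAP 5.2 tabulates and lists important deviations, and SAP 6.4 does the same for concomitant medications. The FAS (SAP 3.5.3) excludes nobody for prohibited therapy.

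**The concern.** Protocol 14.6 offers the efficacy summaries as evidence on whether the effect of study treatment is maintained over 48 weeks. A PASI90 score reached with the help of methotrexate, another biologic or phototherapy is not evidence of that, yet nothing in the plan stops it from being credited to the assigned bimekizumab dose.

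The plan is also uneven. Stopping study drug already makes a subject a non-responder. Two subjects with the same added biologic and the same scores can therefore be classed differently, only because one was withdrawn and the other was not. The response rate then depends partly on a discretionary decision. The continuous summaries have the same feature: multiple imputation fills in missing values only, so scores observed under the added therapy are kept.

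**Working it through.** The plan states no figure that depends on this rule, so there is none to reproduce. The check has two parts.

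**1. Does any rule catch the subject?** Take a subject who starts a Table 7-1 biologic during PS0011, stays on study drug, attends every visit and shows at least 90% PASI improvement.

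| Rule | Outcome for this subject |
|---|---|
| NRI, early discontinuation (SAP 4.2.2) | Not met: still on study drug |
| NRI, missing data (SAP 4.2.2) | Not met: score observed |
| Criterion 7 | Depends on the Investigator's opinion of compliance |
| Criterion 8 | Depends on a judged safety risk; distortion of efficacy is not a ground |
| Protocol 7.8.2 | Withdrawal is optional |
| Criterion 12 | Not met while PASI75 is held; does not act before Week 12 |
| FAS definition | Included |
| Deviation review (SAP 3.4) | Can lead only to PK-PPS exclusion |
| Observed case summary | Uses the same score |

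The subject is a PASI90 responder. If any discretionary rule leads to withdrawal from study drug, the subject becomes a non-responder with no change in scores.

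**2. How far can one subject move a rate?** In a group of n, reclassifying one subject changes the rate by at most 100/n points, and by nothing if the subject would have responded without the added therapy.

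Inputs:
- 240 subjects planned for PS0010 (Protocol 14.8) and six regimens (Protocol 2.2.1). Equal arms are assumed: 240/6 = 40.
- Full roll-over into PS0011 is assumed.
- Week 12 PASI90 rates of 30% to 70% are assumed. The documents give none. The range suits placebo least: a placebo responder stratum could be smaller, and one subject would then weigh more.
- SAP 10.1 splits the PS0010/PS0011 tables by Week 12 responder status, so a whole arm of 40 is not the denominator there. SAP 3.6 pools the two 160mg arms.

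| Group | n | At most, per subject |
|---|---|---|
| Single-arm stratum | 40 × 0.3 = 12 to 40 × 0.7 = 28 | 100/12 = 8.3 to 100/28 = 3.6 points |
| Pooled 160mg stratum | 80 × 0.3 = 24 to 80 × 0.7 = 56 | 100/24 = 4.2 to 100/56 = 1.8 points |
| PS0011 320mg column | 40 + 40 + (24 to 56) = 104 to 136 | 100/104 = 1.0 to 100/136 = 0.7 points |

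The total effect is at most the number of such subjects times 100/n. That number cannot be obtained from the documents.

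**The case against.** **It is a choice of estimand.** SAP 4.2 deals with dropouts and missing data. A score observed under added therapy is not missing, and using it is a recognised approach. SAP and Protocol agree, so there is no conflict between them. This stands in part. However, neither document declares that approach, and the plan already departs from it by counting subjects who stop study drug as non-responders.

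**The rates never measured bimekizumab alone.** Protocol 7.8.1 permits topical corticosteroids, retinoids and vitamin D analogs, and responses on them count. That is true, and permitted topicals are outside this point. Table 7-1 therapies differ because the protocol forbids them.

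**Few subjects will get through.** The therapies are prohibited, subjects are told to consult the Investigator before taking any medication, and criteria 7, 8 and 12 remove some users. A biologic or immunosuppressant is also where criterion 8 is most likely to be applied. This stands as a reason to expect few cases. It does not close the gap, because each medication-related route is discretionary and criterion 12 cannot act on a subject whom the added therapy holds at PASI75.

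**Use stays visible.** The deviation, concomitant-medication and efficacy listings let a reader trace recorded cases. That is so, but no planned output links use to response, and the tabulated rates do not change.

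**Stronger readings.** A reader might infer that the published rates are materially inflated, or might multiply an assumed rate of use into an overall bias. The documents give no rate of use, so only the bound per subject is supported. Nor do they suggest any effect on the primary safety variable, which does not use response status.

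**Conclusion.** The gap is real and minor. Non-response has two triggers, neither covers use of a Table 7-1 systemic antipsoriatic, biologic or phototherapy, and withdrawal for such use is discretionary. A subject kept on study drug can therefore be credited with PASI90 or IGA response. The consequence is confined to secondary and other efficacy summaries in a study without inferential analyses.

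The sizes in the working are upper bounds per subject. They rest on equal arms, full roll-over and an assumed 30% to 70% range for Week 12 PASI90. If nobody used such therapy while on study drug, the rates do not change at all.

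**What to change.** Add to SAP 4.2.2:

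- **Responder variables.** In the NRI summaries, a subject is a non-responder at visits on or after the start of a Table 7-1 systemic antipsoriatic, biologic or phototherapy that could affect psoriasis.
- **Identification.** Reviewers blinded to both PS0010 and PS0011 assignment identify qualifying uses in the SAP 3.4 deviation review, before unblinding. They work to written criteria that also define which brief courses are excluded.
- **Continuous variables.** Values from that date are set to missing before MI. Where LOCF replaces MI, the last value before that date is used.
- **Observed case summaries.** These stay as recorded.
- **Partial or unknown start dates.** The blinded review assigns the earliest visit plausibly affected. The SAP 4.2.1 default is not used here: it can move a year-only or unknown start date to the first dose, which would turn every post-dose PS0011 visit into a non-response.

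SAP 3.11 now reports no changes to the protocol-defined analyses. It should record the added trigger, because Protocol 14.6 defines only two.

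**Cost.** SAP wording, one derived flag and a small blinded review. Protocol 7.8 already requires drug, dates and indication. It does not name phototherapy, so if that is not on the eCRF it must come from the deviation tracker. Stated response rates may be slightly lower, including for a flagged subject who would have responded anyway. A course that is not excluded as brief counts through Week 48 even if it ends sooner, so the criteria for brief courses need care. Continuous means may change little, because MI within treatment group borrows from subjects without added therapy.
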